1 INTRODUCTION

As new lenses come to market it is of interest to compare the performance of the new product to the performance of established products. This study will evaluate the performance of two monthly replacement silicone hydrogel lenses after one month of bilateral wear, in habitual frequent replacement (FRP) soft contact lens (CL) wearers. The established product is CooperVision's Biofinity Sphere (Lens A) and the new product to market is the recently launched Total 30 (lens B) manufactured by Alcon Inc..

2 OBJECTIVES

To evaluate the performance of two monthly replacement silicone hydrogel contact lenses in habitual FRP CL wearers when worn for 1-month.

The primary outcome variables for this study are:

- Lens handling on removal (0-10 scale, 0.5 steps) at 1-month visit

3 HYPOTHESIS

The null hypothesis is that there will be no difference between Lens A and Lens B for the primary outcome variable of lens handling on removal (0-10 scale, 0.5 steps) collected after 1-month of wear.

4 MATERIALS AND METHODS

4.1 STUDY DESIGN

4.1.1 OVERALL DESIGN

This study will be a prospective, randomized, double-masked, single-site, 1-month cross-over design involving bilateral eye daily wear of two different monthly replacement CL types. Each lens will be worn bilaterally for approximately one month.

There are 5 scheduled study visits that take place on 3 different days, including the screening and exit visits:

Visit 1: Screening/eligibility, baseline assessments and fitting of both study lenses

Visit 2: Subject randomization and Dispense of study lens Pair #1 (this will be combined with Visit 1 if participant meets all eligibility criteria at V1)

Visit 3: 1-month follow up of study Pair #1, dispense of study Pair #2

- [REDACTED] 1

Visit 4: 1-month follow up of study Pair #2, and study exit

- [REDACTED]

EXIT: Anticipated to follow immediately after Visit 4 unless participant discontinues early

[REDACTED]
[REDACTED]

4.1.2 RANDOMIZATION

A randomization schedule will determine the order of wear of lens A and lens B for the first and second month, for each participant. Participants will be randomized at the beginning of Visit 2 after eligibility has been confirmed during V1.

A randomization schedule will be generated by CORE's data management team and provided to the unmasked research assistant(s) for the study. It will be included in the final report. Study investigators will remain masked to the randomization schedule until the study is completed and the database is locked.

4.1.3 MASKING

Participants will be masked to the lens assignment. Lenses dispensed to participants may have the foil label completely removed or have all or part of the label obscured. Investigators will be masked as much as possible however it may not be possible to fully mask the investigators, because identifying lens markings may be visible during the biomicroscopy examination.

4.2 STUDY POPULATION

4.2.1 SAMPLE SIZE CALCULATION

The sample size was calculated using data of 'lens handling at removal' ratings collected in a previous study using a 0-10 rating scale. This data showed a standard deviation of paired differences of 1.02. With an alpha level of 0.05 in a paired difference test, and power of 84%, a minimum sample size of 20 participants is recommended in order to determine a statistically significant difference of 0.71 between study lenses , Figure 1.

To account for dropout, up to 25 participants may be randomized and dispensed with study product in total, with the target of at least 20 completing the study.

[figure not shown]

Figure 1: Sample size calculation graph

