10 STATISTICAL ANALYSIS AND DATA MANAGEMENT

10.1 STATISTICAL ANALYSIS

Primary comparisons will be between study lenses (e.g. in-office subjective ratings of lens handling collected after 1 month).

All data will be analyzed by CORE at the University of Waterloo. Unmasked data analysis will be conducted using Statistica, SPSS or other appropriate software. Descriptive statistics will be provided on information regarding baseline variables (age, gender, refractive error distribution, etc.).

Table 7 lists the primary outcome variables and anticipated statistical procedures.

Table 7: Statistical procedures

Variable	Analysis	Statistical test
Subjective ratings	Descriptive and other statistics	Mean, Median*, Standard Deviation, Minimum, Maximum, Frequency count
	Effect of treatment on outcome variable within subjects (comparison between study days)	Wilcoxon matched pairs test
		Mean, Median*, Standard Deviation, Minimum, Maximum, Frequency count
		Wilcoxon matched pairs test

The critical alpha level for statistical significance will be set at 0.05, with no adjustments for multiple comparisons.

All participants who were evaluated will be included in the analysis, unless their removal is agreed by the sponsor due to protocol deviations and/or adverse events. In the event of missing data, individual data points will not extrapolated from the collected data.

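### Does the 84% power in section 4.2.1 need restating because Table 7 plans a Wilcoxon test?

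*Combined protocol and SAP*

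**What the plan says.** The sample size paragraph (section 4.2.1) takes an SD of paired differences of 1.02 from removal-handling ratings in a previous study and sets 0.71 as the difference to detect. It continues: "With an alpha level of 0.05 in a paired difference test, and power of 84%, a minimum sample size of 20 participants is recommended". The test is described only as "in a paired difference test", and the text does not say whether the alpha is one-sided or two-sided. The paragraph points to Figure 1, a sample size graph, which could not be read for this review. Up to 25 participants may be randomised so that at least 20 complete.

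Section 3 gives a non-directional null: "The null hypothesis is that there will be no difference between Lens A and Lens B" on the primary outcome, which is scored from 0 to 10 in steps of 0.5.

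For subjective ratings, Table 7 (section 10.1) gives "Wilcoxon matched pairs test" for the comparison within subjects, and no paired t test appears. On significance, section 10.1 says: "The critical alpha level for statistical significance will be set at 0.05, with no adjustments for multiple comparisons". It does not state sidedness either.

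**The concern.** A power statement should describe the test that will be run. Someone who reads section 4.2.1 together with Table 7 will naturally take 84% as the power of the Wilcoxon test. The inputs are a mean difference and an SD. Those fix the power of a t test under normality, but not the power of a signed-rank test, which also depends on the shape of the differences and on how many are tied or zero on a 0.5-step scale.

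The missing sidedness adds to the doubt, because the same inputs give a clearly higher power one-sided than two-sided. If the 84% had come from a one-sided calculation, or from a test much more powerful than the planned one, 20 completers could be too few for the stated difference.

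**Working it through.** **Inputs.** From section 4.2.1: alpha 0.05, difference 0.71, SD of paired differences 1.02, n = 20 completers, up to 25 randomised. From sections 2 and 3: outcome in 0.5 steps, null of no difference. The documents do not give the shape of the differences, so every shape below is an assumption.

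**Step 1: reproduce the 84%.** For a paired t test, the noncentrality is (0.71 / 1.02) × √20 = 0.696 × 4.472 = 3.11, with 19 degrees of freedom. Power is the probability that a noncentral t variable with these parameters falls beyond the critical value.

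| Variant, n = 20 | Power |
|---|---|
| Paired t, two-sided | 83.95% |
| Paired t, one-sided | 91.2% |
| Normal approximation, two-sided | 87.6% |
| Normal approximation, one-sided | 92.9% |

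Of these four, only the two-sided paired t test matches. A one-sided t test would reach 84.4% with 16 participants, so it would not lead to 20. Strictly, the two-sided t test first reaches 84.0% at n = 21 (85.8%); n = 20 matches after rounding.

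**Step 2: Wilcoxon power if the differences are normal.** The large-sample efficiency of the signed-rank test relative to the t test is then 3/π = 0.955. The effective sample size is 20 × 0.955 = 19.1, which gives 82.1%. Simulation of the exact two-sided signed-rank test gives 82.2% (200,000 trials). When the differences are put on the 0.5-step scale, with zeros dropped and ties corrected, power is 82.6% (60,000 trials). The shortfall is 83.95 − 82.2 = 1.8 points on a continuous scale and 83.95 − 82.6 = 1.4 points on the protocol's own scale. In participants, by the same efficiency, 20 / 0.955 = 20.9, so about one more completer gives the same power.

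**Step 3: other shapes.** Two-sided Wilcoxon with mean 0.71 and SD 1.02 held fixed:

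| Assumed shape | Continuous, n = 20 | 0.5 steps, n = 20 | 0.5 steps, n = 25 |
|---|---|---|---|
| Uniform | 76.3% | 82.4% | 90.8% |
| Normal | 82.2% | 82.6% | 90.9% |
| Logistic | 85.1% | 84.3% | 91.7% |
| t, 5 df | 87.9% | 86.5% | 93.5% |
| Laplace | 88.3% | 86.1% | 92.9% |

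The 0.5-step columns apply to this outcome, and at n = 20 they lie on both sides of 84%. The list is not exhaustive. With a t distribution on 3 df, power is 94.7% on a continuous scale and about 93% in 0.5 steps. With skewed exponential differences on a continuous scale it is 85.1% (left) and 91.5% (right).

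**Step 4: the t test depends on shape too.** For the same skewed exponential shapes on a continuous scale, two-sided t-test power at n = 20 is 78.4% (left) and 96.3% (right). The 84% is a planning value under normality whichever test is named.

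**The case for a change.** The best case for a change is that it costs a sentence or two and removes a real ambiguity. The text of section 4.2.1 gives no test and no sidedness. The figure matches a t test that the analysis section never mentions, and the planned test has no power figure of its own. A reader trying to reproduce the calculation could get 84% or 91% from the same inputs.

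Those facts stand, but they carry little weight:

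- The generic term in section 4.2.1 covers both a paired t test and a Wilcoxon test, so the two sections do not contradict each other.
- The non-directional null in section 3 settles the number of sides, and the reproduction agrees.
- Figure 1 belongs to section 4.2.1 and may name the test and the sides. Only the text can be said to omit them.
- The t test is the best match but is not proven to be the source. Wilcoxon on the 0.5-step scale gives 84.3% for a logistic shape, so stating as fact that the 84% belongs to a t test would go beyond the evidence.
- A second power figure in the protocol would rest on an assumed shape. A range such as 76% to 88% would mislead: its lower end comes from a continuous uniform shape that gives 82.4% in 0.5 steps, and heavier tails go above its upper end.

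**Conclusion.** This is missing detail that a statistician fills in correctly from the plan itself: a two-sided test, with the sample size found by the usual paired t formula under normality and the analysis done by the rank-based counterpart. That is common practice for bounded rating scales. The stated 84% reproduces at 83.95%.

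If the paired differences are normal, the planned Wilcoxon test has about 82% to 83% power with 20 completers, a gap of 1 to 2 points or about one participant. For the five shapes tabulated in 0.5 steps, power runs from 82% to 87% with 20 completers and from 91% to 94% if all 25 complete. These figures rest on the stated SD of 1.02 and on shapes that the documents do not give.

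The 84% is not shown to be wrong for either test. Naming the test and the sides would be tidy reporting, but it would not alter the sample size, the primary analysis or any conclusion. No change to the plan is needed.

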4.2.2 NUMBER OF PARTICIPANTS

Participants will be recruited using CORE records and advertising approved by the UW Office of Research Ethics. Approximately 25 eligible participants may be dispensed with study products,

with a target of at least 20 completing the study. Informed consent will be obtained for all participants prior to their enrolment in the study and prior to any study data collection.

4.2.3 INCLUSION AND EXCLUSION CRITERIA

A person is eligible for inclusion in the study if he/she:

1. Is at least 17 years of age and has full legal capacity to volunteer;
2. Self-reports having had a full eye examination within the previous 2 years;
3. Has read and signed an information consent letter;
4. Is willing and able to follow instructions and maintain the appointment schedule;
5. Is a habitual wearer of frequent replacement contact lenses;
6. Anticipates no difficulty wearing the contact lenses for 6 days/week and 8 hours/day during the study;
7. Has refractive astigmatism no higher than -0.75DC in each eye;
8. Can be successfully fit with both study lens types;
9. Achieves at least 0.4 logMAR VA monocularly and at least 0.2 logMAR VA binocularly with each study lens type.

A person will be excluded from the study if he/she:

1. Is participating in any concurrent clinical research study;
2. Has any known active* ocular disease and/or infection;
3. Has an unstable systemic condition that in the opinion of the investigator may affect vision or contact lens comfort across the 2-month study duration;
4. Is using any systemic or topical medications in an irregular routine that in the opinion of the investigator may affect vision or contact lens comfort across the 2-month study duration;
5. Has known sensitivity to the diagnostic sodium fluorescein to be used in the study;
6. Is an employee of the Centre for Ocular Research & Education.

* For the purposes of this study, active ocular disease is defined as infection or inflammation which requires therapeutic treatment. Mild (i.e. not considered clinically relevant) lid abnormalities (blepharitis, meibomian gland dysfunction, papillae), corneal and conjunctival staining and mild dry eye are not considered active ocular disease. Neovascularization and

corneal scars are the result of previous hypoxia, infection or inflammation and are therefore not active.

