4.5 STUDY PROCEDURES

A summary of the study procedures to be conducted at scheduled visits is listed in Table 4. More procedure details are included for each visit in the following sections.

Table 4: Summary of procedures to be conducted at scheduled visits

	V1 Screen Fit of study CL	V2 Dispense first study lens	V3 1-month follow- up first study lens, dispense second study lens	V4 1-month follow- up second study lens	Exit
Consent process	X				
Subject age & sex	X				
CL history (brand & power) [^] and lens wear schedule	X		X	X	
Health & medication	X	X	X	X	
Review any problems with eyes/study lenses		X	X	X	
	X				X (OR SUBJ. REFRACTION)
	X				
	X				
Randomization		X			
	X				
Dispense study CLs		X	X		
	X	X	X	X	
	X	X	X	X	
		X	X	X	
			X	X	
		X	X		
			X	X	
	X	X*	X	X	X*
Study CL collection			X	X	
Study completion and Exit					X

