3. The participant will be assigned a randomization number (Randomization ID#) by the unmasked research assistant.

4. The first pair (lens pair #1) of study contact lenses (either Lens A or Lens B) will be selected by the unmasked research assistant according to the randomization table.

5. Lens pair #1 will be provided to participants in a manner which does not unmask the participant or investigator, as described in Section 4.1.3.

6. The participant will insert the lenses.

7. The contact lenses will be allowed to settle for 5 minutes.

8. [REDACTED]

c) [REDACTED]
[REDACTED]
[REDACTED]
[REDACTED]
[REDACTED]
[REDACTED]
[REDACTED]
[REDACTED]

11. The participant will be asked to wear the study lenses for at least 8 hours per day and 6 days per week.

12. [REDACTED]
[REDACTED]

13. The participant will be provided with instructions for the safe wear & care of the contact lenses as well as sufficient care product supply.

14. [REDACTED]
[REDACTED]
[REDACTED]

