4.5.3 VISIT 3 1-MONTH FOLLOW-UP PAIR #1 & DISPENSE PAIR #2

Participants will be asked to attend this visit after wearing Lens Pair #1 for at least 6 hours. This visit will occur 28-31 days (inclusive) after visit 2.

[figure not shown]
The study procedures are outlined below:

1. Review changes to medical history and medications.
2. The participant will be asked to score their subjective responses and rate their typical wearing schedule and reflect on their overall satisfaction [REDACTED]
[REDACTED] during the month for the lens performance items listed below:

a) [REDACTED]
[REDACTED]
[REDACTED]

d) Overall satisfaction with handling for lens removal (0 – 10 scale, 0.5 steps);

e) [REDACTED]
[REDACTED]
[REDACTED]

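### Should current wearers of either study lens be kept out of, or analysed apart in, the removal-handling comparison?

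*Combined protocol and SAP*

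**What the plan says.** Eligibility (section 4.2.3) requires that a participant "Is a habitual wearer of frequent replacement contact lenses". None of the six exclusions, the last of which is "Is an employee of the Centre for Ocular Research & Education", concerns the brand worn. Section 1 describes Lens A as the established product and says "the new product to market is the recently launched Total 30".

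Habitual brand is recorded at Visit 1: Table 4 in section 4.5 lists "CL history (brand & power". Randomization (section 4.1.2) concerns sequence only: "A randomization schedule will determine the order of wear of lens A and lens B".

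Section 10.1 gives a Wilcoxon matched pairs test for the subjective ratings, with no covariate or subgroup in the readable part of Table 7. On baseline data it says: "Descriptive statistics will be provided on information regarding baseline variables (age, gender, refractive error distribution, etc", an open-ended list.

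On exposure before scoring, section 4.5.2 says: "The participant will be asked to wear the study lenses for at least 8 hours per day and 6 days per week". In section 4.5.3 participants reflect on their satisfaction "during the month for the lens performance items listed below", with words blacked out immediately before that phrase. Sections 2 and 3 place the primary rating at the 1-month visit. Section 4.1.3 masks participants to lens assignment.

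**The concern.** The endpoint is a self-rating of a manual skill. For someone who already wears one of the study lenses, the comparison sets a practised lens against a new one. Pairing removes a participant's general rating level. It does not remove an effect specific to one lens, because that effect has the same sign in A-minus-B whichever lens is worn first.

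Lens A is established and Lens B is new, so an excess of Lens A wearers is plausible, and familiarity could then tilt the result toward Lens A. With a target of 20 completers, a handful of such participants could matter. As written, the plan does not say how a reader would learn whether the conclusion depends on them, although the brand data are collected.

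**Working it through.** **The plan's own figure.** Section 4.2.1 gives an SD of paired differences of 1.02, a difference of 0.71, alpha 0.05, n = 20 and power 84%. For a two-sided paired t-test the noncentrality is 0.71/1.02 × √20 = 3.11 on 19 degrees of freedom, and power is 83.9%. The stated figure reproduces.

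**Model for a familiarity shift.** Let shares pA and pB of participants habitually wear Lens A and Lens B, and let each rate their own lens h points higher. None of these values is in the documents; all are assumptions.

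- Mean bias in A minus B = (pA − pB) × h
- SD of differences = √(1.02² + h² × [(pA + pB) − (pA − pB)²])

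Results for n = 20, paired t. Power is for a true 0.71 advantage of Lens B:

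| pA | pB | h | Bias | SD | Rejection rate if otherwise equal | Power |
|---|---|---|---|---|---|---|
| 0 | 0 | 0 | 0 | 1.020 | 5.0% | 84% |
| 10% | 0 | 0.2 | 0.02 | 1.022 | 5.1% | 82% |
| 20% | 0 | 0.5 | 0.10 | 1.039 | 6.9% | 70% |
| 30% | 10% | 0.5 | 0.10 | 1.063 | 6.9% | 68% |
| 20% | 20% | 0.5 | 0 | 1.068 | 5.0% | 80% |
| 20% | 0 | 1.0 | 0.20 | 1.096 | 12% | 51% |
| 40% | 0 | 1.0 | 0.40 | 1.132 | 32% | 21% |

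If Lens A is truly better by 0.71, power rises instead: 91% at pA = 20%, h = 0.5. A simulation of the signed-rank test with differences in 0.5 steps gives similar values (11% and 49% at pA = 20%, h = 1.0).

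Three features of the table matter.

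- The bias depends on pA − pB, so equal shares leave only extra variance.
- The alarming rows need h = 1.0, which exceeds the 0.71 target and is about one whole SD of the differences. That shift would have to survive roughly 28 × 6/7 = 24 removals of each lens.
- The added variance assumes that the earlier study behind the 1.02 contained no such wearers, which section 4.2.1 does not say.

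**Would the natural remedy work?** Suppose the analysis is repeated without the k current wearers among 20 pairs, all of them Lens A wearers, so that f = pA = k/20. The expected movement of the estimate is f × h. The chance movement, with no familiarity effect at all, has SD 1.02 × √(1/(20 − k) − 1/20).

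| k (f) | Chance SD | Expected move, h = 0.5 | Ratio | Expected move, h = 1.0 | Ratio |
|---|---|---|---|---|---|
| 2 (10%) | 0.076 | 0.05 | 0.7 | 0.10 | 1.3 |
| 4 (20%) | 0.114 | 0.10 | 0.9 | 0.20 | 1.8 |
| 8 (40%) | 0.186 | 0.20 | 1.1 | 0.40 | 2.1 |

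At h = 0.5 the estimate would move in the wrong direction in about 26%, 19% and 14% of trials. The reduced set of 18, 16 or 12 pairs has power of about 79%, 74% or 59% for 0.71, and a 95% CI half-width of 0.51, 0.54 or 0.65 against 0.48 with all 20.

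**Would stratification work?** No. Every participant wears both lenses, so balancing wear order by brand leaves the shift where it is.

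**The case for a change.** The strongest case for a change is that the remedy is almost free: one sentence in section 10.1 and one table row, using data already in hand. If the analysis is chosen only after unmasked data have been seen, it can be called selective. A month of wear need not erase practice if the rating looks back over the whole month, and masking does not help, because practice does not require recognising the lens.

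Much of this stands. Current wearers are not excluded, their brand is known, the crossover does not remove a lens-specific shift, and an analysis specified in advance is more credible than one added later.

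Three parts do not carry through. The argument about the first days of wear rests on a sentence whose qualifying words are redacted, so the recall period cannot be read from it. The direction is not established: dissatisfaction with a current lens could reverse the shift. And low cost does not make the analysis informative. The primary result would stay as it is, and there is no threshold at which a movement of the estimate would count as evidence with about 20 pairs.

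**Conclusion.** No change to the plan is needed. Section 2 sets the target as lens performance in habitual frequent-replacement wearers, and the null in section 3 concerns the rating itself. A current wearer's liking for a known lens is part of the difference in that population. The rejection rates above 5% are errors only if one substitutes a familiarity-free question that the trial does not ask. Excluding these wearers at screening would narrow the stated population, which is a fair trade-off for the sponsor to weigh and not a correction.

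The possible size ranges from nothing to a bias of 0.40, wholly on assumed shares of 10 to 40% and shifts of 0 to 1.0, with all familiar wearers on one lens. At a moderate shift of 0.5, a repeat analysis without them could not tell the effect from chance.

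The sensible minimum, a count of habitual lens (A, B or other), already fits the open-ended baseline summary in section 10.1. If the analysts also show the paired difference with and without current wearers, it should be labelled exploratory and read with the chance movement above in mind.
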